### A.2.1. Placebo Control

Only 2 of these studies included a placebo arm: TREAT (for DA) and Amgen Canadian (for EpoA). In both cases, the mean estimated change from baseline in Hb was 0.3 g/dL after approximately 20 weeks. Most of the other studies were noninferiority trials that used either EpoA or DA as the reference group; they did not include a placebo group. See the methods below for handling this gap in available data.

### A.2.2. Baseline and Target Hb Levels

Since the primary outcome variable is constrained by screening limits as well by therapeutic target ranges, the treatment effect for an effective drug (i.e., one increasing Hb into the target range) would naturally vary according to the average baseline Hb in the sample, guided somewhat by inclusion criteria, as well as the target Hb level. The treatment effect would be lower for the low-target studies than for the high-target ones. As Figure A 1 shows, the DD group of studies has lower average baseline Hb and higher treatment effect than the NDD studies. This suggests a moderator effect of baseline Hb in the 16 study arms included here: the higher the average baseline Hb level, the smaller the treatment effect. We interpret this result cautiously, however, because baseline Hb and DD/NDD status are almost completely confounded.

**Figure A 1. Treatment Effect by Baseline and Target Hemoglobin Levels**

Data cutoff: 01DEC2017 E:/Proj/Akebia/Programs/f\_nim\_meta\_v001.R (last run: 12/22/2017, 14:13) meta\_analysis\_mods1.png

### A.3. Statistical Methods

The most important decisions in conducting a meta-analysis concern both the input data and the statistical method. The choice of input data (presented in [Table A 2](#)) depends on what studies to include and how to handle unavailable data. We faced a problem because so few previous studies had placebo arms and some of the studies had missing information about the pre and post treatment outcome variances and correlations. Our choice of statistical method, fixed effects model, was based on several packages in R (metafor, MAd) and accompanying literature.

#### A.3.1. Derivation of Input Statistics

We used the data collected from publications and applied the following rules to fill in the desired baseline and post-baseline means and standard deviations. Post-baseline refers to assessment after at least 20 weeks of treatment:

1. Compute the standard deviations from standard errors or half-widths of the reported confidence intervals.
2. Compute post-baseline means based on baseline and reported changes from baseline.
3. Use available data to impute missing means and SDs, making the post-baseline SD the same or slightly larger than SD for the baseline.
4. Compute correlation between baseline and post-baseline means (based on three arms with a standard error for the difference).
5. Set remaining pre-post correlations to 0.30, splitting the difference between the observed values from 0.14 to 0.58, to compute SD for the change scores. The largest study, TREAT, was “penalized” with a lower correlation of 0.10.

#### A.3.2. Placebo Adjustment

Three study arms had a placebo control arm. For the remaining 13 study arms, we introduced a hypothetical placebo arm with a mean of 0.3 and sample size and SD equivalent to the active treatment comparison arm. In this counterfactual scenario, we imagine each study had a placebo arm of size, baseline, and variance equal to the active treatment arm. Since there is general agreement that the placebo effect is essentially negligible, adding an imaginary placebo arm with small change from baseline will not distort the results away from the null hypothesis of no treatment effect.

**Table A 2. Input Dataset for Meta-analysis**

| ID | Study Arm      | DD  | Hb Target | Active treatment |                |                         | Placebo control |                |                         | Pre-post corr 1a |
|----|----------------|-----|-----------|------------------|----------------|-------------------------|-----------------|----------------|-------------------------|-----------------------------|
|    |                |     |           | N                | Mean BL (g/dL) | Mean Change (SD) (g/dL) | N               | Mean BL (g/dL) | Mean Change (SD) (g/dL) |                             |
| 1  | TREAT-DA       | No  | high      | 2012             | 10.4           | 2.00 (1.56)             | 2026            | 10.3           | 0.30 (1.56)             | 0.1                         |
| 2  | Affymax-OM1    | No  | high      | 328              | 10.0           | 1.50 (0.85)             | 328             | 10.0           | 0.30 (0.85)             | 0.3                         |
| 3  | Affymax-OM2    | No  | high      | 328              | 10.0           | 1.70 (0.85)             | 328             | 10.0           | 0.30 (0.85)             | 0.3                         |
| 4  | Affymax-DA     | No  | high      | 327              | 10.0           | 1.39 (0.85)             | 327             | 10.0           | 0.30 (0.85)             | 0.3                         |
| 5  | Roche-DA       | No  | high      | 162              | 10.2           | 1.81 (1.03)             | 162             | 10.2           | 0.30 (1.03)             | 0.3                         |
| 6  | Roche-MI       | No  | high      | 162              | 10.2           | 2.10 (1.03)             | 162             | 10.2           | 0.30 (1.03)             | 0.3                         |
| 7  | Akizawa-DA     | No  | high      | 161              | 9.2            | 2.80 (1.11)             | 161             | 9.2            | 0.30 (1.11)             | 0.3                         |
| 8  | Akizawa-Epo    | No  | low       | 160              | 9.2            | 0.90 (1.07)             | 160             | 9.2            | 0.30 (1.07)             | 0.3                         |
| 9  | Amgen202-DA    | No  | high      | 129              | 9.3            | 2.70 (0.99)             | 129             | 9.3            | 0.30 (0.99)             | 0.5                         |
| 10 | Amgen202-Epo   | No  | high      | 37               | 9.8            | 2.20 (1.01)             | 37              | 9.8            | 0.30 (1.01)             | 0.6                         |
| 11 | AmgenDial-Epo1 | Yes | high      | 201              | 7.4            | 3.80 (2.15)             | 201             | 7.4            | 0.30 (2.15)             | 0.3                         |
| 12 | Amgen211-DA    | Yes | high      | 91               | 8.8            | 2.70 (1.38)             | 91              | 8.8            | 0.30 (1.38)             | 0.1                         |
| 13 | AmgenCAN-Epo1  | Yes | low       | 44               | 6.9            | 3.30 (1.18)             | 48              | 7.1            | 0.30 (1.40)             | 0.3                         |
| 14 | AmgenCAN-Epo2  | Yes | high      | 38               | 7.1            | 4.60 (1.55)             | 48              | 7.1            | 0.30 (1.40)             | 0.3                         |
| 15 | AmgenDial-Epo2 | Yes | high      | 35               | 8.2            | 3.50 (2.15)             | 35              | 8.2            | 0.30 (2.15)             | 0.3                         |
| 16 | Amgen211-Epo   | Yes | high      | 31               | 8.5            | 3.70 (1.43)             | 31              | 8.5            | 0.30 (1.43)             | 0.3                         |

BL: baseline ; CAN: Canada; corr: correlation; DA: darbepoetin alfa; DD: dialysis dependence; Epo: epopoetin alfa; Hb: hemoglobin; MI: Mircera; OM: Omontys SD: standard deviation

The placebo statistics for records in red are reported for a true placebo control arm.

a. The correlation between baseline and post-treatment sample means was derivable for study arms with IDs of 9, 10, and 12. In all other cases, it was assumed to be 0.1 or 0.3.

Data cut: 01Dec2017

E:\proj\akebia\programs\l\_meta1.sas v.002 (last run: 01/17/2018, 13:33) l\_meta1.rtf (page 1 of 1)

### A.3.3. Justification of the Model

Meta-analytic techniques are often used to obtain overall estimates of treatment effects. When at least 25 studies are available for analysis, there is sufficient information to provide confidence in the combined estimates, confidence intervals, and statistical tests. When a sufficient number of studies is available, both the between and within-study variability can be estimated and used in calculating an overall treatment effect. Some statisticians favor random effects meta-analytic methods in this situation; however, most meta-analyses are not based on a large number of studies and the fixed effects approach becomes necessary. Moreover, the weights assigned to

Statistical Analysis Plan AKB-6548-CI-0014 and AKB-6548-CI-0015

[figure not shown]
studies in random effects analyses are similar across studies allowing small studies to have the same effect on the overall estimates as large studies. Therefore, many statisticians favor fixed effects models even when a lot of studies are available.

Fixed effects meta-analysis approaches are based on the following set of assumptions: there is one true effect size; inferences are based on the studies included in the meta-analysis and cannot be formally extended beyond the collection of studies; the properties of the estimates, tests and confidence intervals are based on the total number of subjects across the studies rather than the number of studies; and the weights are approximately proportional to the sample size or follow-up time, in time-to-event studies. In this analysis, the 16 study arms range in size from 35 subjects to 2026 subjects per group favoring the use of the fixed effects approach.

#### **A.4. Results of Meta-analysis**

See [Figure A 2](#) for the results of the specified meta-analysis model fit to the 16 study arms, augmented with placebo adjustment, with an overall mean as the sole fixed effect. The estimated placebo-adjusted change from baseline in Hb is 1.58 g/dL with a lower 95% confidence interval bound of 1.53 g/dL. We have also used this method to perform separate meta-analyses on the DD and NDD studies. The overall treatment effect estimates and 95% confidence intervals in g/dL were 1.50 (1.44, 1.55) and 3.17 (2.95, 3.38) for the NDD and DD subgroups, respectively.

**Figure A 2. Forest Plot of Placebo-adjusted Treatment Effect of ESAs on Hemoglobin**

Data cutoff: 01DEC2017  
 E:/Proj/Akebia/Programs/f\_nim\_meta\_v002.R (last run: 01/02/2018, 12:59) E:/Proj/Akebia/Programs/Figures/f\_nim\_meta/meta\_analysis\_forest0.png

**A.5. Rationale for Margin**

Based on the 95% lower confidence bounds for the pooled and subgroup overview analyses, the percent of treatment effect that would be preserved varies according to the choice of noninferiority margin (see Table A 3). A noninferiority margin of -1.0 g/dL would preserve a third of the treatment effect for CI-0014 (not dialysis dependent [DD], ESA-naive) study and two-thirds of the treatment effect for the CI-0016 (dialysis dependent, -ESA-naive) study. A noninferiority margin of -0.75 g/dL would preserve a half of the treatment effect for CI-0014 (not dialysis dependent, ESA-naive) study and three-quarters of the treatment effect for the CI-0016 (dialysis dependent, ESA-naive) study.

Statistical Analysis Plan AKB-6548-CI-0014 and AKB-6548-CI-0015

**Table A 3. Percent of Treatment Effect Preserved by Study Type and Margin**

| Analysis Population
(Number of Study Arms) | 95% Lower
Bound (g/dL) | Noninferiority Margin (g/dL) |       |      |
|---|---------------------------|------------------------------|-------|------|
|   |                           | -1                           | -0.75 | -0.5 |
| All studies pooled (16)                       | 1.53                      | 35%                          | 51%   | 67%  |
| Not dialysis dependent (10)                   | 1.44                      | 31%                          | 48%   | 65%  |
| Dialysis dependent (6)                        | 2.95                      | 66%                          | 75%   | 83%  |

Table created manually.

## APPENDIX B. MISSING DATA (INCLUDING MULTIPLE IMPUTATION)

This appendix describes the methods planned to handle missing data for the primary and secondary efficacy outcomes. Standard multiple imputation, where imputation of missing values is based on the group to which the subject was randomized, will be used for all analyses except the tipping point analysis. The tipping point analysis is described below to explore deviations from the assumptions that missing data would follow observed treatment arm trends.

The literature for handling missing data in noninferiority studies is limited and the considerations differ from those for a superiority study. For example, in a superiority study one can impute all missing data using the data obtained from the placebo group under a reference based imputation. Such an approach is generally considered a conservative analysis in the setting of a superiority study as imputation of missing data in the treated group is based on the assumption that no treatment was received. In this noninferiority setting, reference-based imputation is not a conservative approach as efforts to make the vadadustat group behave more like the darbepoetin alfa group are anti-conservative. We are not aware of any published statistical proposal for “conservative” imputation in a noninferiority study, but [Wiens and Rosenkranz, \(2013\)](#) demonstrated that standard imputation performs best for the handling of missing data in noninferiority studies.

### B.1. Overall Approach

Missing data will be imputed through multiple imputation under fully conditional specification (FCS) with  $M = 100$  imputed datasets. The general framework for the process is as follows:

- In the first step of the analysis, all missing values will be imputed for hemoglobin outcomes, all other efficacy outcomes, and any covariates to be used in the models. The primary outcome and secondary outcomes will be derived from the imputed values of Hb in the primary efficacy period (PEP) and secondary efficacy periods (SEP). The variables in the imputation model are delineated in [Table B 1](#).
- A set of pre-assigned seeds are shown in [Listing B 1](#). These seeds will be used for all imputations required in both efficacy and MACE safety analyses.
- All multiple imputation will be implemented using FCS.
- The type of model used for FCS will be tailored to the variable with missing outcome data. Specifically, the following types of regression will be used:
  - Continuous variables: regression
  - Binary variables: logistic regression
  - Ordinal classification variables: response logistic regression
  - Nominal classification variables: response logistic regression
- Rubin’s rule will be used to obtain the final result which can be computed using PROC MIANALYZE.
- A total of 40 iterations will be used for the burn-in.
- Before inclusion in the model, variables will be assessed for collinearity using the condition index and regression coefficient variance-decomposition matrix computed using PROC REG in SAS.

Statistical Analysis Plan AKB-6548-CI-0014 and AKB-6548-CI-0015

This appendix provides SAS code for the imputations for all variables of interest. This code, and the associated seeds, will be used to generate the analysis datasets.

To ensure uniformity across all analyses, the change from baseline and binary outcomes derived from Hb measures will be imputed by calculating the imputed value of the continuous measure and then deriving the change score or binary outcome (Ratitch, 2016). This procedure will be adjusted if the imputation model proves inconsistent with the substantive model.

**Table B 1. Outcome Variables and Covariates in the Multiple Imputation Models**

| Type       | Variable a | Description  | Baseline, Post, Outcome | Levels |
|------------|-----------------------|--|-------------------------|--------|
| Continuous | HBBL                  | Baseline Hb  | Baseline                | n/a    |
| Continuous | HBS1                  | Hb in Weeks 2-8  | Post                    | n/a    |
| Continuous | HBS2                  | Hb in Weeks 10-20  | Post                    | n/a    |
| Continuous | HBS3                  | Hb in PEP (Weeks 24-36)  | HBCHGS3, HBRNGS3        | n/a    |
| Continuous | HBS4                  | Hb in SEP (Weeks 40-52)  | HBCHGS4, HBRNGS4        | n/a    |
| Continuous | TIBCBL                | Baseline TIBC  | Baseline                | n/a    |
| Continuous | HEPCNBL               | Baseline hepcidin  | Baseline                | n/a    |
| Continuous | FERRBL                | Baseline ferritin  | Baseline                | n/a    |
| Continuous | UACRBL                | Baseline uACR (PRO2 only)  | Baseline                | n/a    |
| Continuous | CRPBL                 | Baseline CRP   | Baseline                | n/a    |
| Continuous | TSATBL                | Baseline TSAT  | Baseline                | n/a    |
| Continuous | EGFRBL                | Baseline eGFR (PRO2 only)  | Baseline                | n/a    |
| Continuous | TIBCS3                | TIBC in PEP (Weeks 24-36)  | Post                    | n/a    |
| Continuous | HEPCNS3               | Hepcidin in PEP (Weeks 24-36)  | Post                    | n/a    |
| Continuous | FERRS3                | Ferritin in PEP (Weeks 24-36)  | Post                    | n/a    |
| Continuous | UACRS3                | uACR in PEP (Weeks 24-36) (PRO2 only)  | Post                    | n/a    |
| Continuous | CRPS3                 | CRP in PEP (Weeks 24-36)   | Post                    | n/a    |
| Continuous | TSATS3                | TSAT in PEP (Weeks 24-36)  | Post                    | n/a    |
| Continuous | EGFRS3                | eGFR in PEP (Weeks 24-36) (PRO2 only)  | Post                    | n/a    |
| Continuous | ESABL                 | Baseline ESA dose  | Baseline                | n/a    |
| Continuous | TDIALBL               | Time on dialysis prior to Screening Visit 1 (INNO2 only)                               | Baseline                | n/a    |
| Continuous | AGE                   | Age  | Baseline                | n/a    |
| Binary     | SEX                   | Sex male   | Baseline                | 2      |
| Nominal    | RACEGR2               | Race: white, black, other  | Baseline                | 3      |
| Binary     | TRT01P                | Randomized treatment   | Baseline                | 2      |
| Binary     | DIALTYP               | Dialysis type (INNO2 only)   | Baseline                | 2      |
| Binary     | DMHX                  | History of diabetes mellitus   | Baseline                | 2      |
| Binary     | CVHX                  | History of CV disease (coronary artery disease, MI, stroke, HF)                        | Baseline                | 2      |
| Binary     | CVOTHHX               | History of other CV disease (DVT, Arterial Thrombosis, PE, Vascular Access Thrombosis) | Baseline                | 2      |
| Ordinal    | SMOKEHX               | Smoking history  | Baseline                | 3      |
| Binary     | STRAT3P               | NYHA CHF class 0/1 vs. 2/3   | Baseline                | 2      |
| Nominal    | STRAT2A               | Geographical region  | Baseline                | 3      |

Table created manually.

- a. Variables names are preliminary and will be adjusted to comply with CDISC.

## **B.2. Multiple Imputation of all Missing Values**

Multiple imputation will be used to create M datasets for the primary and secondary efficacy analyses. The imputation relies on the use of FCS and model code provided in [Exhibit B 1](#) below. The examples of code come from version 9.4 of SAS. Code will be modified slightly as needed according to software updates and compatibility with actual data.

The variables in [Table B 1](#) will be used to populate macro variables &BINVARS for all binary variables, &NOMVARS for all nominal variables, and &ORDVARS for all ordinal variables. The variables are imputed sequentially in the order specified in the VAR statement.

Except where specified, imputation procedure will rely on the default behavior of FCS for the method and predictor covariates. The variable being imputed is sampled from a posterior distribution conditional on all the values, observed and imputed, of variables to the left of it in the VAR statement and all the observed-only values of variables to its right. If no FCS statement is included for a variable with missing data, the default method depends on the variable type. The regression method is default for continuous variables, and the discriminant function method is default for categorical variables (list in CLASS statement).

## **B.3. Primary Efficacy Analysis**

The primary efficacy analysis is based on the difference between the changes from baseline (average pretreatment Hb) to the PEP (average of up to 4 per-visit observations in Weeks 24 to 36). The noninferiority analysis is based on a margin of -0.75 g/dL applied to the difference in mean change between vadadustat and darbepoetin alfa. To establish noninferiority, the lower limit of the confidence interval of the mean change in vadadustat minus the mean change in darbepoetin alfa must be -0.75 g/dL or higher. ANCOVA with multiple imputation for missing data will be used to calculate the 95% confidence interval of the difference.

Multiple imputation will rely on the method of fully conditional specification (FCS). Under this assumption, data for each variable with missing values will be imputed with a separate regression model allowing for all available data to be used in the imputation process. For continuous variables, the regression method will be used for imputations. For categorical variables, logistic regression models will be used for binary outcomes, ordinal logistic regression for ordinal responses, and nominal response logistic regression for nominal responses. The models for imputation under each of these conditions will be described in this appendix.

The output from the multiple imputation procedure is M complete datasets. For the primary analysis, these datasets are analyzed using ANCOVA and the code in [Exhibit B 2](#) below. The M estimates of the difference in the change from baseline in the PEP are then “combined” using PROC MIANALYZE to obtain a final estimate and its associated significance level.

### **B.3.1. SAS Code for Standard Multiple Imputation using FCS**

This section describes the procedures to impute missing values for the primary efficacy analysis. Missing values are imputed separately for each treatment group using a BY statement in PROC MI.

### Exhibit B 1. SAS Code for Standard Imputation of Missing Values for the Primary Efficacy Analysis

---

```

proc mi data=&INDAT. nimpute=&M. seed=&SEED1. out=&OUTDAT.;
  by TRT;
  class &BINVARS. &NOMVARS. &ORDVARS.;

  var
    STRAT2_HF STRAT3_REG
    SEX RACE AGE HX_CV4 HX_CV_OTH HX_DM ESA_BL SMOKE_BL
    HEP_BL FERR_BL TIBC_BL CRP_BL TSAT_BL HB_BL
    HB_1 HB_2 HEP_3 FERR_3 TIBC_3 CRP_3 TSAT_3
    HB_3 HB_4;
  /* continuous - primary */
  fcs plots=trace reg ( HB_3) nbiter=40;

  /* continuous example - other */
  fcs reg ( HB_1) nbiter=40;

  /* binary or ordinal example */
  fcs logistic( SEX / link=logit likelihood=augment) nbiter=40;

  /* nomial example */
  fcs logistic (RACE/link=glogit likelihood=augment) nbiter=40

  run;

```

---

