#### **Exhibit B 4. SAS Code for Tipping Point Analysis**

---

```
proc mi data=&INDAT. (where=(TRT="VADA")) nimpute=&M.
    seed=&SEED2. out=&OUTDAT.;
class &BINVARS. &NOMVARS. &ORDVARS.;
var
    STRAT2_HF STRAT3_REG
    SEX RACE AGE HX_CV4 HX_CV_OTH HX_DM ESA_BL SMOKE_BL
    HEP_BL FERR_BL TIBC_BL CRP_BL TSAT_BL HB_BL
    HB_1 HB_2 HEP_3 FERR_3 TIBC_3 CRP_3 TSAT_3 HB_3
    HB_4;
fcs reg ( HB_3) nbiter=40;
mnar adjust ( HB_3 / shift=&S. );
run;
```

---

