**Listing B 1. Random Seed Assignment for all Planned Analyses**

| Analysis Category                            | Analysis ID | Analysis Detail                          | PRO 2 TECT |                      | INNO 2 VATE |                      |
|--|-------------|--|-----------------------|----------------------|------------------------|----------------------|
|  |             |  | CI-0014 a  | CI-0015 b | CI-0016 c   | CI-0017 d |
| Primary Efficacy, Secondary, & All Subgroups | PE          | Impute missing Hb & covariates           | 635320903             | 1987393372           | 32552474               | 1864814524           |
| Primary Efficacy - Sensitivity               | PES1        | Rescue definition 1 (narrow)             | 429585122             | 1373196336           | 1027066416             | 928246872            |
|  | PES2        | Rescue definition 2 (broad-on-treatment) | 549618248             | 1156395436           | 477818637              | 2071955541           |
|  | PES3        | Tipping point                            | 340408944             | 1747908400           | 1450082522             | 216479710            |

Analyses that use a shared seed between CI-0014 and CI-0015 or CI-0016 and CI-0017 are highlighted in yellow.

a. Seeds for CI-0014 are generated based on a master seed of 10014.

b. Seeds for CI-0015 are generated based on a master seed of 10015.

c. Seeds for CI-0016 are generated based on a master seed of 10016.

d. Seeds for CI-0017 are generated based on a master seed of 10017.

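### The imputation code in SAP Exhibits B 1 and B 4 omits the baseline and PEP eGFR and uACR that SAP Table B 1 requires for CI-0014 and CI-0015

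*SAP*

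**What the plan says.** SAP B.1 points to one list for the imputation model: "The variables in the imputation model are delineated in" Table B 1. That table has rows for "Baseline eGFR (PRO2 only") and "Baseline uACR (PRO2 only"), then "uACR in PEP (Weeks 24-36) (PRO2 only") and the matching row for eGFR in the PEP. The mark restricts these four rows to CI-0014 and CI-0015.

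The code has a different list. In Exhibit B 1 the baseline laboratory part of the VAR statement is "HEP_BL FERR_BL TIBC_BL CRP_BL TSAT_BL HB_BL". The post-baseline part, which Exhibit B 4 repeats for the tipping point analysis, runs "HB_1 HB_2 HEP_3 FERR_3 TIBC_3 CRP_3 TSAT_3 HB_3" and then the Hb value for the secondary efficacy period (SEP). Neither eGFR nor uACR appears in either exhibit.

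On the status of the code, SAP B.1 says: "This code, and the associated seeds, will be used to generate the analysis datasets". SAP section 1 treats the printed code as fixing what each analysis is meant to be. SAP B.2 describes the exhibits as examples but allows only slight changes, for software updates or compatibility with the data. Listing B 1 assigns a single imputation run to "Primary Efficacy, Secondary, & All Subgroups". SAP section 11 defines subgroups by baseline eGFR (cut at 15) and baseline uACR (cut at 300), analyzed by the primary and secondary methods.

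**The concern.** Table and code give two different imputation models for the primary endpoint, and no rule says which one prevails. B.2 ties the order of imputation to the VAR statement, so the seeds in Listing B 1 do not determine the imputed values until the list is settled.

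The four variables are not incidental here. The protocol's background section attributes anemia in CKD mainly to reduced erythropoietin production by the kidney, so eGFR is a plausible predictor of Hb. It may also be related to missingness: a kidney transplant requires permanent discontinuation (protocol Amendment 7-COL, 7.5.5), and SAP 2.2 plans no laboratory assessments after end of treatment. If kidney function predicts both, leaving it out weakens the missing-at-random assumption. The rescue sensitivity analyses in SAP 9.1.5, which set further Hb values to missing, rely on the imputation model more heavily than the primary analysis does.

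The subgroups are more exposed. Imputations made without the variable that later splits the data can reflect that split only through correlated covariates.

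**Working it through.** **Step 1. Compare the two lists.**

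| Source | Count |
|---|---|
| Variables in Table B 1 | 32 |
| Of these, INNO2VATE only (time on dialysis, dialysis type) | 2 |
| Applying to PRO2TECT: 32 − 2 | 30 |
| Variables in the VAR statement of Exhibit B 1 | 25 |
| Plus treatment, entered through the BY statement | 26 |
| In the table but not in the code: 30 − 26 | 4 |

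The four are baseline uACR, baseline eGFR, PEP uACR and PEP eGFR. Nothing in the code is absent from the table. With the four added, the VAR statement has 25 + 4 = 29 variables, and with treatment 30, which matches the table.

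**Step 2. Could they enter another way?** B.2 fills the macro variables from the binary, nominal and ordinal rows of Table B 1. All four missing variables are typed as continuous, so only the VAR statement can bring them in.

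**Step 3. The plan's own figure, for scale.** With SD 1.5 and 925 per arm (SAP 2.7), the standard error of the difference is 1.5 × √(2/925) = 0.070 g/dL. For a margin of 0.75, power exceeds 99.9%, and 85 per arm would give 90%. That agrees with the stated power above 90% and is not affected by this point.

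**Step 4. Size in the primary analysis.** The documents give no missing fraction, no slope of Hb on kidney function and no shift, so every input here is an assumption. The bias in one arm is f × b × d, where

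- f is the fraction with no PEP Hb;
- b is the Hb slope per SD of kidney function, given the other imputation variables;
- d is the difference in kidney function between missing and observed subjects, in SDs.

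Bias common to both arms cancels in the difference.

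- Arms differ in missingness by 5 to 10 points, b = 0.15 to 0.25, d = 0.5 to 1.0. Low: 0.05 × 0.15 × 0.5 = 0.004. High: 0.10 × 0.25 × 1.0 = 0.025 g/dL.
- Only one arm affected, f = 0.05 to 0.20, b = 0.1 to 0.3, d = 0.5 to 1.0. Low: 0.05 × 0.1 × 0.5 = 0.0025. High: 0.20 × 0.3 × 1.0 = 0.06 g/dL.

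The largest value is 0.06/0.75 = 8% of the margin.

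**Step 5. Subgroup treatment differences.** Let m be the fraction missing in the subgroup, equal in both arms. If the other covariates carry none of the subgroup signal, the subgroup difference moves toward the overall one by m × (overall effect − subgroup effect). For m = 0.05 to 0.30 and an assumed gap of 0.2 to 0.5 g/dL, that is 0.05 × 0.2 = 0.01 to 0.30 × 0.5 = 0.15 g/dL. With no gap and equal missingness it is zero. With unequal missingness there can be a shift without any gap; the documents give nothing from which to size it.

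**The case against.** The best defense is that the exhibits are not the final program. B.2 calls them examples, B.1 screens variables for collinearity before inclusion, and the two INNO2VATE-only variables are missing too, which suggests a common core for four trials. A programmer who follows Table B 1 would include the four variables and no harm would arise. This stands in part: the consequence is conditional on running the code as printed. It does not remove the contradiction, because B.1 commits to the code and the latitude in B.2 does not extend to adding four predictors.

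Several stronger conclusions are tempting, and the documents do not support them.

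- A reader might infer that low-eGFR subjects are imputed as though their kidney function were average. The model conditions, within arm, on baseline, earlier and later Hb, ESA dose, iron indices and CRP. Only residual information is lost, and titration of both arms to a common Hb range should reduce it further.
- A reader might infer that imputed Hb is biased upward. That requires missing subjects to have lower eGFR and lower eGFR to mean lower Hb after this conditioning. Neither is shown.
- A reader might count dialysis as a main route to missing data. Protocol 7.5.2 (Amendment 7-COL) says progression to dialysis is not a criterion for withdrawal from the study or from study medication.
- A reader might infer that subgroup results shrink by the missing fraction. That describes the association of eGFR with Hb. Section 11 estimates treatment differences, which move only under the conditions in Step 5, and it presents them as descriptive.

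It is also fair to say that the PEP values add little for PEP Hb. Protocol 9.3.5 draws eGFR at Weeks 28 and 36 and uACR at Week 28, visits at which the blood count is taken as well. A subject with no PEP Hb will nearly always lack both.

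The MMRM and the tipping point analysis give some protection against a wrong imputation model, although Exhibit B 4 has the same omission.

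**Conclusion.** The concern holds as a contradiction between SAP Table B 1 and Exhibits B 1 and B 4. It is exact and complete: four variables required for PRO2TECT, none in the code. The textual finding is certain; the consequences depend on the code being run as printed.

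In that case only subjects with no Hb in the PEP or SEP are affected, and the primary ANCOVA does not contain eGFR or uACR under either version. The sizes in Step 4 rest wholly on assumed slope, shift and missingness, and they make a change in the noninferiority conclusion unlikely. The eGFR and uACR subgroups have more at stake, but their treatment differences shift only if the effect varies with eGFR or uACR (then toward the overall result) or if missingness differs between arms. It should be corrected before database lock because it is a plain inconsistency in the primary imputation model and cheap to remove. It is not a threat to the primary result.

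**What to change.** For CI-0014 and CI-0015, add baseline eGFR, baseline uACR, PEP eGFR and PEP uACR to the VAR statements in Exhibits B 1 and B 4. State in SAP B.1 that Table B 1 governs where table and code differ. The baseline values carry most of the gain for PEP Hb; the PEP values mainly help SEP Hb. If the omission was intended, remove the four rows from Table B 1 and give the reason.

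A log scale for uACR is an optional suggestion, in keeping with the geometric means in SAP E.1.3. Table B 1 does not state it.

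The cost is four variable names in each of two code blocks and one sentence. No new data are needed and the seeds can stay as listed.
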